If DLTs are observed in the first two consecutive patients of a previously untested dose level, subsequent enrolment to that cohort will be stopped. The Bayesian logistic regression model will be re-run to confirm that the dose-level still fulfils the EWOC criterion. Decision will be made whether the next patients will be enrolled on the same dose level, or if they will be enrolled to a lower dose level. [Figure 3.1: 1](#) shows how the decision of dose escalation is made.

[figure not shown]

Figure 3.1: 1: Escalation Decision – Combination of clinical and statistical expertise

BI 836880 infusion will be repeated every 3 weeks. In the case the patient shows a stable disease or even a response, the administration of BI 836880 can be continued up to disease progression or until intolerable toxicity has been recorded. In specific cases an intra-patient dose escalation can be granted (see [section 4.1.3](#)).

Once a MTD has been reached it is foreseen to enroll up to 12 patients on this dose level to enlarge the group of patients treated on proposed RP2D. A minimum of 12 patients must have tumour lesions evaluable for Dynamic contrast-enhanced (DCE)-MRI to allow a better interpretation of a pharmacodynamics (vascular) effect of BI 836880. Confirmation of the RP2D will be made based on all available safety, PK and Pharmacodynamics (PD) data at all treatment cycles and all dose levels.

In case of anti-tumor activity signals in a given tumor type, DSB can take the decision for a trial expansion to recruit patients with the same tumor type with the aim to generate safety and preliminary efficacy data specific to such disease. 2-3 tumor type expansion cohorts are planned. Up to a total of 20 patients may be recruited in each tumor type expansion cohort and will be treated according to same [Flow Chart](#) as patient in previous cohorts. This is to confirm RP2D in patient with specific tumor type according to study objective and to prepare further Phase II studies. This change will be implemented with a further amendment to this protocol.

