Patients, who received at least two treatment cycles, deeming to have clinical benefit from treatment and tolerated the drug BI 836880 well (i.e. do not show any DLT) could be allowed to receive increased dose. Such decision will be taken in a case by case manner on request by Investigator and confirmation by DSB based on actual patient profile. Intra-patient dose escalation can be repeated; however the dose can only be increased to highest tested safe dose.

For patients with an intra-patient dose escalation(s) all assessments will be done according to instructions for the first cycle at start of treatment with BI 836880 and intensive PK-sampling, [REDACTED]

[REDACTED] will be conducted (see [Flow Chart](#) and [Appendix 10.4](#)) and patients have to be closely followed for any adverse events. Therefore patients have to come to the clinic during the first course of intra-patient dose escalation every week. Additional visits are needed at day 2 and at day 3 of the 1st cycle of dose escalation.

The above-mentioned procedures will be followed also in case of further intra-patient dose escalations.

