5.3.2 Maximum Tolerated Dose (MTD)

The MTD may be considered reached if the probability that the true DLT rate is in target interval (16% - 33%) is sufficiently large. For detailed definition see statistical part ([section 7](#)). The DSB may recommend stopping the dose finding phase after the criterion for MTD is fulfilled. Further patients may be included to confirm the MTD.

If next dose level is recommended by the statistical model; however, the efficacy is considered sufficient at current dose level, the DSB may decide to include additional number of patients at this dose level, declare this dose as RP2D and no further dose escalation will happen.

Decision on next steps (dose escalation, de-escalation or cohort expansion) will be made by a Data Safety Board (DSB) based on all available safety data, including DLT information from

last cohort as described above but also findings from subsequent courses as well as other data (e.g. PK/PD data) when available.

Based on the overall data after all patients on proposed RP2D have been treated for at least 1 cycle, the DSB will make a final determination of RP2D.

Before the conclusion of the dose escalation phase and prior to the start of the expansion cohort, up to 12 patients should have been treated on the proposed RP2D.

After determination of RP2D, 2-3 expansion cohorts could be started to treat a specified patient population based on preliminary efficacy data and according to DSB decision.

All DSB decisions of dose escalation, and to open a new cohort for recruitment will be communicated to Investigators. Once MTD and RP2D is defined this information will be send to authorities.

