3	V1	1	Before start of BI 836880 infusion	-0:05	x		X (3x)	X (3x)
			Start of BI 836880 infusion	0:00				
			Before end of infusion	1:30**			X (3x)	X (3x)
			Immediately after end of infusion*	1:30**	x			
		2		24:00	x			X (3x)

Proprietary confidential information © 2019 Boehringer Ingelheim International GmbH or one or more of its affiliated companies

Table 10.4: 1(cont'd) Blood sampling scheme for PK, [REDACTED] in courses 1, 2, 3 and from course 4 onwards (cont.)

Course	Visit	Day	Time Point (hh:min)	CRF Time / planned time	PK: BI 836880	[REDACTED]	ECG	BP
4	V1	1	Before start of BI 836880 infusion	-0:05	x	[REDACTED]	X (3x)	X (3x)
			Start of BI 836880 infusion	0:00		[REDACTED]		
			Before end of infusion	1:30**		[REDACTED]	X (3x)	X (3x)
			Immediately after end of infusion*	1:30**	x	[REDACTED]		
			0.5h after the end of infusion	2:00	x	[REDACTED]		
			1.5h after the end of infusion	3:00	x	[REDACTED]		
			3.5h after the end of infusion	5:00	x	[REDACTED]		
			6.5h after the end of infusion	8:00	x	[REDACTED]		
		2		24:00	x	[REDACTED]	X (3x)	
	V2	8		168:00	x	[REDACTED]		X (3x)
	V3	15		336:00	x	[REDACTED]		X (3x)
5-12	V1	1	Before start of BI 836880 infusion	-0:05	x	[REDACTED]	X (3x)	X (3x)
			Start of BI 836880 infusion	0:00		[REDACTED]		
			Before end of infusion	1:30**		[REDACTED]	X (3x)	X (3x)
EOT***					x	[REDACTED]	X (3x)	X (3x)
EoR***					x	[REDACTED]		X (3x)
FU1***					x	[REDACTED]		

* within 5 min after the end of infusion

** PTM of 1:30 according to an infusion duration of 90 min. If the infusion duration should be shorter (or longer), the PK sample has to be taken in any case immediately after the end of the infusion/ the ECG has to be conducted shortly before end of infusion and the actual sampling time needs to be recorded in the eCRF. Subsequent PK samples (in C1, C2 and C4) have to be taken 0.5h, 1.5h, 3.5h and 6.5h after the end of the infusion.

*** in case of an intra-patient dose escalation the 1st cycle with the higher dose will follow cycle one at the start of treatment with BI 836880 with regards to sampling, (PK, [REDACTED])

**** No samples will be collected after data base lock and the trial is completed (see [Section 6.2.3.5](#))

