6. GENERAL ANALYSIS DEFINITIONS

6.1 TREATMENT(S)

The starting dose of the study is BI 836880 40mg every three weeks, and dose escalation decision will be made by Data Safety Board (DSB).

The following treatment period will be defined:

- Screening: from the date of informed consent to the date of first study medication intake -1 day.
- On-treatment: from the date of first infusion of study drug to the date of last study drug administration + 42 days, i.e., actual on-treatment period + residual effect period (REP).
- Post-study: from the last day of on-treatment period + 1 day onwards

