7.4 PRIMARY ENDPOINT(S)

The primary endpoint is to assess the MTD based on the number of patients presenting DLTs during the MTD evaluation period. The primary analysis is for the determination of the MTD. The purpose of this analysis is to summarize and document the data that led to the selection of the MTD. Therefore, an overall summary of DLTs (see CTP section 5.3.1 for the definition of DLTs) which occurred during the MTD evaluation period will be provided for each dose cohort from the dose finding cohort treated set. Patients, if any, who did not complete the MTD evaluation period for reasons other than DLT will be excluded from the analysis of the primary endpoint.

A summary of the number of patients with DLTs overall in any course will be also given by initial treatment and displayed in a similar format to the summary of DLTs occurring in the MTD evaluation period.

The analysis of the MTD is based on a Bayesian logistic regression model (BLRM) guided by the escalation with overdose control principle. The MTD is defined as the highest dose for a given schedule that is expected to cause less than 25% risk of the true DLT rate being above or equal to 33% during the MTD evaluation period. Estimation of the MTD during the dose escalation phase of the study will be based upon the estimation of the posterior probability of the incidence of DLT in toxicity categories during the MTD evaluation period for all evaluable patients. The model to be used is specified in CTP section 7.

The posterior probabilities that the toxicity rates of each dose level fall into the categories specified in CTP section 7 will be displayed.

[figure not shown]

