7.7 EXTENT OF EXPOSURE

Treatment exposure will be primarily summarized by the total on-treatment time and has been defined in [section 5.4](#) of this TSAP.

Treatment interruptions before permanent discontinuation will not be excluded. Summary statistics for treatment time by each dose level and the dosage of BI 836880 over time will also be provided.

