The frequency of patients with adverse events will be summarised by highest CTC grade (grades 1, 2, 3, 4, 5 and all grades), treatment, primary system organ class and preferred term for each of the following AE tables as well as relatedness of AEs to treatment and seriousness:

- All AEs
- Drug-related AEs
- AEs leading to dose reduction
- Drug related AE leading to dose reduction
- AEs leading to treatment discontinuation
- Drug-related AEs leading to treatment discontinuation
- Drug related AEs leading to treatment discontinuation or dose reduction
- AEs leading to death
- Serious AEs
- Drug related serious AEs
- Non-serious AE with higher than 5% occurrence rate
- DLTs

All tables will be sorted by system organ classes (SOC) according to the standard sort order specified by the European Medicines Agency (EMA). Preferred terms (PTs) will be sorted by frequency (within SOC).

The above tables will be repeated with the project defined grouping of AE terms. Details of the project defined groupings are defined in the technical TSAP. In these tables the grouped AEs will replace the original PTs for all AEs that are included within the grouped term. The grouped AE categories will then be tabulated along with all remaining MedDRA PTs, sorted by descending frequency.

A reference table presenting the entire project defined groupings and MedDRA PTs within each grouping will also be produced.

Additional AE tables will be produced for AEs of special interest (hepatic injury as defined in CTP section 5.3.8.1 and dose limiting toxicities as defined by 5.3.1), providing further details on highest CTC grade, action taken with study drug and time to first onset of AE.

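### SAP 7.4 shows any-course DLTs only by starting dose, so an escalated patient's first DLT appears in a lower-dose row and not at the dose being given

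*SAP*

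**What the plan says.** **The table.** SAP 7.4 plans, beside the primary first-cycle summary and in a similar format: "A summary of the number of patients with DLTs overall in any course will be also given by initial treatment".

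**Dose increases within a patient.** Protocol 4.1.3 says that patients who have had at least two cycles, appear to benefit clinically and "tolerated the drug BI 836880 well (i.e. do not show any DLT) could be allowed to receive increased dose". The investigator requests the increase and the DSB confirms it case by case. It can be repeated, up to the highest dose tested and found safe. The protocol treats the new dose as a fresh start: assessments follow first-cycle instructions (4.1.3), and for sampling the footnote to Table 10.4: 1 says "the 1st cycle with the higher dose will follow cycle one at the start of treatment with BI 836880".

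**What else the SAP offers on dose.**
- Section 6.1 defines one treatment period, not split by dose: "On-treatment: from the date of first infusion of study drug to the date of last study drug administration + 42 days".
- Section 7.8.1 labels the first-cycle safety analysis by initial dose and states no dose rule for the all-cycles analysis. It lists a DLT table by treatment without saying what treatment means after an increase. Its additional tables, which cover DLTs, are described as "providing further details on highest CTC grade, action taken with study drug and time to first onset of AE".
- Section 7.7 covers exposure, not events: "Summary statistics for treatment time by each dose level and the dosage of BI 836880 over time will also be provided".

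**Use of later-cycle safety data.** Protocol 3.1: "Confirmation of the RP2D will be made based on all available safety, PK and Pharmacodynamics (PD) data at all treatment cycles", and at all dose levels. Protocol 5.3.2 has DSB decisions draw on DLT information from the "last cohort as described above but also findings from subsequent courses as well as other data".

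**The concern.** The any-course table exists to show toxicity that the first cycle misses. For an escalated patient it shows that toxicity beside a dose already taken for at least two cycles without a DLT, and not beside the dose in use when the DLT began. The displacement has a direction: low-dose rows gain events and higher-dose rows lose them. The higher doses are the likelier RP2D candidates, and the RP2D is to be confirmed on safety data from every cycle and dose level. No visible SAP table states DLTs by dose at onset, so a reader of the report could not recover the other view from the planned tables.

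The SAP is dated 21 June 2017. Protocol amendment 2, which added the detailed guidance for escalated patients, is dated 14 February 2017. The case was therefore known when the SAP was finalised.

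**Working it through.** The documents give no figure for this table, so there is nothing to reproduce. The check is a comparison of rules followed by counts.

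**Step 1: order of events.** Under Protocol 4.1.3 a patient who has shown a DLT does not qualify for an increase. So, for any escalated patient, the first DLT starts after the first increase.

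**Step 2: row assignment.** Under SAP 7.4 the row is the initial treatment, so that DLT falls in the starting-dose row. The dose in use at onset is higher, unless the patient was reduced back to the starting dose in the meantime. Protocol 4.1.4 allows each patient one reduction.

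**Step 3: effect on the primary analysis.** The primary endpoint counts DLTs in the first cycle, and an increase needs at least two cycles. No primary DLT can be affected.

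**Step 4: size in one row.** Cohort sizes come from Protocol Table 10.6: 1, scenario 6: 2 patients at 40 mg, 2 at 120 mg, 3 at 360 mg and 3 at 720 mg. Assume one patient is raised in a single step to 720 mg, has a DLT there, and no one else has a DLT. By dose at onset, a row's denominator is every patient with at least one infusion at that dose, so the 720 mg row holds 3 + 1 = 4.

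| Patient started at | Row | By initial treatment | By dose at onset |
|---|---|---|---|
| 40 mg | 40 mg | 1/2 (50%) | 0/2 (0%) |
| 40 mg | 720 mg | 0/3 (0%) | 1/4 (25%) |
| 360 mg | 360 mg | 1/3 (33%) | 0/3 (0%) |
| 360 mg | 720 mg | 0/3 (0%) | 1/4 (25%) |

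**Step 5: precision.** Exact 95% intervals are 0.013 to 0.987 for 1/2, 0 to 0.842 for 0/2, 0 to 0.708 for 0/3 and 0.006 to 0.806 for 1/4. They overlap almost entirely. What changes is where the event is seen, not a well-estimated rate.

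**The case against.** **The table is not wrong on its own terms.** It says it is by initial treatment and it is. It counts each patient once, with fixed denominators. A table by dose at onset counts some patients twice and uses denominators that include patients selected for good tolerance. It also rests on a convention, because a DLT after an increase may reflect accumulation from the earlier dose. All of this stands. It is why the existing table should stay, and why one cannot say that the starting dose played no part.

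**A reader might infer that the DSB or the RP2D decision would be misled.** The documents do not show that. SAP 7.4 gives the purpose of its analysis as documenting the data behind the MTD. The DSB works from outputs prepared for its meetings (Protocol 7.4), with minimum data set in its charter (3.1.1). It confirms each increase individually (4.1.3). Events meeting the DLT criteria are reported as AESIs within 24 hours (5.3.8.1, 5.3.9). The loss is in the trial report, not demonstrably in the decision.

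**A reader might also infer a change in what the dose-toxicity model permits, or set the rows against the 16% to 33% target interval.** Both belong to first-cycle DLTs, and neither is planned for any-course counts. Nor can a frequency be given, since the documents do not say how many patients were escalated.

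**The 40 mg example is demanding.** With the cohorts in step 4 and the waiting times in Protocol 3.1, clearing 720 mg takes about (2 + 3) + 3.3 + 3.6 + 3.6 = 15.5 weeks from the first 40 mg dose, or about 13.5 for the second 40 mg patient, before any DSB or recruitment time. The patient must stay on treatment, benefiting and DLT-free, throughout. The 360 mg example needs less and shows the same shift.

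**Unseen text could close the gap.** SAP 7.8.1 leaves the all-cycles dose label open, and its rule for merging AE episodes does consider treatment changes. The technical TSAP and redacted sections might settle it. Nothing visible does.

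**Conclusion.** The point holds as a gap in a supportive, descriptive summary. In the visible plan, the one any-course DLT table with a stated dose rule attributes the first DLT of every escalated patient to the starting dose, which is lower than the dose at onset unless the dose was reduced back. There is no companion table. One such event in rows of 2 or 3 moves a DLT from the higher-dose row to the lower-dose row, as in 1/2 and 0/3 against 0/2 and 1/4.

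This does not touch the first-cycle MTD analysis, is not a labelling error, and is not shown to have altered any DSB decision. It matters only if at least one escalated patient has a DLT, which the documents do not tell us. The illustration assumes the scenario 6 cohort sizes and a single-step increase. The conclusion also assumes that the technical TSAP and redacted sections contain no summary by dose at onset. It is a cheap improvement worth making.

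**What to change.** In SAP 7.4, keep the summary by initial treatment and add the same summary by dose at the last infusion before DLT onset. Use as denominator the patients with at least one infusion at that dose, and show beside it the treatment time at that dose, which SAP 7.7 already plans. Footnote that escalated patients appear in more than one row, that they are selected for tolerance, and that attribution to the last dose cannot exclude cumulative toxicity. Leave the first-cycle MTD analysis as it is.

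The cost is one sentence in the SAP and one derived variable, built from infusion records already used for compliance (SAP 7.3) and exposure (SAP 7.7). No protocol amendment or new data is needed. The drawbacks are small cells and overlapping rows, which the footnote discloses.

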A summary of the prior distribution is provided in [Table 7.1:1](#). Additionally, the prior probabilities of DLT at different doses, as well as the corresponding probability of under-, targeted and overdosing, are shown in [Table 7.1:2](#). Graphically, the prior medians with accompanying 95% credible intervals are shown in [Figure 7.1:1](#). As can be seen from both, the Table and the Figure, the prior medians of the DLT probabilities are in-line with the prior medians derived from the weakly informative prior, and the uncertainty around the medians is large, showing the low amount of information this prior provides. This is also supported by the prior sample size, i.e. the information contained in the prior. This is approximately equal to 1.2 patients, i.e. less than or around half of the weight the first cohort in the study will have.

Table 7.1: 1 Summary of prior distribution

Prior Component	Mixture Weight	Mean vector	SD vector	Correlation
1: Weakly inf.	0.900	-0.333 0.647	2.000, 1.000	0.000
2: High Tox	0.050	0.419 -0.274	2.000, 1.000	0.000
3: Low Tox	0.050	-3.316 0.042	5.000, 0.010	0.000

Table 7.1: 2 Prior probabilities of DLT at selected doses

Dose	Probability of true DLT rate in			Mean	SD	Quantiles		
	[0–0.16)	[0.16–0.33)	[0.33–1]			2.5%	50%	97.5%
40	0.877	0.049	0.074	0.069	0.172	<.001	0.001	0.703
120	0.813	0.071	0.116	0.104	0.208	<.001	0.006	0.812
360	0.685	0.110	0.205	0.176	0.258	<.001	0.043	0.899
720	0.515	0.153	0.332	0.274	0.295	<.001	0.148	0.944
1250	0.269	0.164	0.566	0.444	0.318	0.005	0.410	0.975

Doses printed in bold face meet the overdose criterion ($P(\text{overdose}) < 0.25$)

[figure not shown]

Figure 7.1: 1 Prior medians and 95% credible intervals

The MTD may be considered reached if the following criteria is fulfilled

1. At least 1 DLT on the trial and either
2. At least 6 patients haven been treated at the MTD and the posterior probability of the true DLT rate in the target interval (16%-33%) is above 50%, OR
3. At least 18 patients in the trial with 6 patients have been treated at MTD.

Statistical model assessment

The model was assessed using two different metrics:

1. Hypothetical data scenarios: for various potential data constellations as they could occur in the actual trial, the maximal next doses as allowed by the model and by the 100% escalation limit are investigated. Data scenarios thus provide a way to assess the “on-study” behaviour of the model.

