7.3.1 Primary endpoint analyses

In order to determine the MTD the occurrence of a DLT in the first cycle will be assessed on an individual patient level. The MTD will be determined as described in [section 7.1](#).

Based on the data observed in the trial other models might be considered either additionally or replacing the primary model. For feasibility or other reasons a different dose might be considered as the recommended dose for Phase II.

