4. CHANGES IN THE PLANNED ANALYSIS OF THE STUDY

5. ENDPOINT(S)

5.1 PRIMARY ENDPOINT(S)

The objective of this study is to determine the safety and tolerability of BI 836880. The primary endpoint is the determination of the maximum tolerated dose (MTD) of BI 836880 based on the number of patients with dose-limiting toxicities (DLTs) during the first treatment cycle. The DLT is defined in section 5.3.1 of the CTP.

The MTD is defined as the highest dose with less than 25% risk of the true DLT probability being above 33%, and may be considered reached if the probability that the true DLT rate is in target interval (16%-33%) is sufficiently large during the MTD evaluation period.

The DLT evaluation period is defined as the time within 3 weeks after first administration of study treatment. The evaluation period will be extended to two more weeks if treatment is delayed due to a drug related AE, For further details, please see CTP section 5.3.1.

Patients, who have not completed first cycle of treatment for other reason than DLT, will be replaced. Patients who were replaced during the MTD evaluation period will not be considered for MTD determination. Those patients that have completed the MTD evaluation period without having been replaced will be referred to as patients evaluable for MTD.

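### SAP 5.1 and 7.4 define the MTD by the overdose limit alone and omit the protocol 7.1 criteria, so the primary endpoint has two rules that can name different doses

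*SAP*

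**What the plan says.** The SAP defines the MTD twice. Section 5.1: "The MTD is defined as the highest dose with less than 25% risk of the true DLT probability being above 33"%. It adds that the MTD may be considered reached when the probability of the 16%-33% interval is sufficiently large, without giving a threshold. Section 7.4: "The MTD is defined as the highest dose for a given schedule that is expected to cause less than 25% risk" of a true DLT rate at or above 33%. The difference between above 33% and at or above 33% is immaterial for a continuous posterior. Neither section gives a minimum number of patients at the dose, a minimum number of DLTs or a trial size.

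Protocol 7.1 gives all of these. The MTD may be considered reached under these criteria:

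- Criterion 1: "At least 1 DLT on the trial and either" one of the next two.
- Criterion 2: "At least 6 patients haven been treated at the MTD and the posterior probability of the true DLT rate in the target interval" is above 50%.
- Criterion 3: "At least 18 patients in the trial with 6 patients have been treated at MTD".

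Both routes need 6 patients at the dose. Protocol 7.3.1 makes this the primary analysis: "The MTD will be determined as described in" section 7.1. SAP 3 says the SAP rests on protocol section 7. SAP 7.4 cites that section for the model and the toxicity categories, but not for the criteria that declare an MTD.

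**The concern.** The model yields a posterior for any dose, given or not, and SAP 7.4 plans to display posteriors by dose level. The potential levels in protocol 4.1.3 include 1000 and 1250 mg. As patients accumulate at one dose with few DLTs, the estimated risk at the next dose falls and can drop below 25% with nobody treated there. The SAP sentence then selects that higher dose, while protocol 7.1 can be satisfied only at a dose with 6 patients.

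This is the primary endpoint. A programmer or report author working from SAP 5.1 and 7.4 could label as MTD a dose that rests on extrapolation and lies above the one the trial studied. At the least, the report would show a dose that meets the SAP's stated definition but differs from the declared MTD.

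**Working it through.** **Model (protocol 7.1).** logit p(d) = log α + β·log(d/d*). The prior on (log α, log β) is the three-component normal mixture of Table 7.1:1: weights 0.90, 0.05, 0.05; means (−0.333, 0.647), (0.419, −0.274), (−3.316, 0.042); SDs (2, 1), (2, 1), (5, 0.01); correlations 0. With x DLTs in n patients at each dose, the likelihood is L = ∏ p(d)^x·(1 − p(d))^(n − x). The overdose risk at dose d is ∫1{p(d) ≥ 0.33}·L·π dθ ÷ ∫L·π dθ, computed on an 801 × 801 normal-quantile grid per component.

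**Which reference dose?** The protocol prints d* = 720 mg, but its own figures do not fit that value. Component 1 is stated to have a median DLT rate of 20% at 720 mg.

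- d* = 1250: logit = −0.333 + e^0.647 × ln(720/1250) = −0.333 + 1.910 × (−0.552) = −1.387, so p = 0.200.
- d* = 720: logit = −0.333, so p = 0.418.

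**Reproducing the protocol's overdose figures with d* = 1250:**

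| Source | Printed | Recomputed |
|---|---|---|
| Table 7.1:2, prior at 40 / 120 / 360 / 720 / 1250 mg | 0.074 / 0.116 / 0.205 / 0.332 / 0.566 | 0.072 / 0.114 / 0.205 / 0.335 / 0.568 |
| Table 10.6:1, scenarios 1-7, current dose | 0.013 / 0.278 / 0.013 / 0.194 / 0.575 / 0.025 / 0.224 | 0.015 / 0.276 / 0.013 / 0.188 / 0.565 / 0.024 / 0.224 |

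The largest difference is 0.010 (scenario 5). With d* = 720 the tables fail: the prior at 720 mg is 0.568 against 0.332, and scenario 7 is 0.384 against 0.224. Results are shown under both values.

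**Comparing the two rules.** The data sets are assumed for illustration. Each starts from 0/2 at 40, 0/2 at 120 and 0/3 at 360 mg (7 patients), with nobody at 1000 mg.

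| Data at 720 mg | N | Protocol 7.1 at 720 mg | Overdose risk at 1000 mg, d* = 1250 | Same, d* = 720 |
|---|---|---|---|---|
| 1/12 | 7 + 12 = 19 | criteria 1 and 3 met | 0.161 | 0.279 |
| 1/18 | 7 + 18 = 25 | criteria 1 and 3 met | 0.099 | 0.186 |

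In the 1/12 case with d* = 1250, the risk is 0.008 at 720 mg, 0.161 at 1000 mg and 0.354 at 1250 mg. The highest dose under 25% is 1000 mg, with no patients, whereas 720 mg is the only dose with 6 or more. With d* = 720 the risk of 0.279 exceeds 25%, so both rules give 720 mg. In the 1/18 case the two rules part under either value; with d* = 720 the risk at 1250 mg is 0.328, so 1000 mg is again the dose named.

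**Limits of the examples.** With d* = 1250, 1/9 at 720 mg (N = 16) already gives 0.222 at 1000 mg, so reaching 1/12 assumes that the DSB expanded the 720 mg cohort, which protocol 4.1.3 permits. With d* = 720, the same calculation gives a risk of 0.343 at 720 mg after the lead-in data alone, so the overdose limit would not have allowed that step. The d* = 720 column therefore tests the wording on final data; it is not a path the design would follow from these cohorts.

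**The case against.** The strongest reply is that the SAP should not be read alone. SAP 3 rests on protocol section 7, protocol 7.3.1 sends the determination to 7.1, and 7.1 requires 6 patients at the MTD by either route. SAP 7.4 also says its purpose is to document the data behind a selection already made. This stands as far as it goes: read together, the documents exclude an untreated MTD. It does not remove the conflict. The highest-dose selection rule appears as a definition only in the SAP, 7.4 cites protocol section 7 for other matters, and 7.1 is phrased permissively.

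A second reply is that SAP 5.1 also asks for a sufficiently large target-interval probability. In the 1/12 case with d* = 1250 that probability is 0.318 at 1000 mg and 0.139 at 720 mg. If the unstated threshold is the protocol's 50%, the SAP names no dose as reached, while the protocol accepts 720 mg through its 18-patient route. The two rules still disagree.

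Third, the first example depends on d*. That is correct; the second does not.

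Some tempting illustrations fail. Data scenario 6 has no DLT, so criterion 1 bars any declaration. With 1/6 at 720 mg, N is 13 and the target probability is 0.291 (d* = 1250), so neither route is met. The early stop in protocol 5.3.2 lets the DSB "declare this dose as RP2D and no further dose escalation will happen"; that concerns the RP2D, which protocol 7.3.1 allows to differ from the MTD.

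**Conclusion.** The SAP's stated rule for the primary endpoint differs from the protocol's, and the two can name different doses. That is a wrong stated rule and not only missing detail. A reader might infer that the trial will, or legitimately can, report an MTD that no patient received. The documents do not support that, because protocol 7.1 and 7.3.1, on which the SAP says it is based, rule it out.

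The size is shown by example: overdose risk at untreated 1000 mg of 0.161 after 1/12 at 720 mg (d* = 1250), and of 0.099 or 0.186 after 1/18 (d* = 1250 or 720). These rest on the printed prior, the assumed cohort data and a literal reading of SAP 5.1 and 7.4. No frequency is claimed for how often the rules would diverge in practice. The mismatch between the printed d* and the protocol's own prior medians and tables is a separate discrepancy, and it affects any rerun of the model.

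**What to change.** In SAP 5.1 and 7.4, state one rule: the MTD is the highest dose with P(DLT rate ≥ 33%) < 25% among doses that meet all the protocol 7.1 criteria. Write those criteria out:

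- at least 1 DLT on the trial;
- at least 6 patients at that dose, counted as evaluable for MTD as SAP 5.1 defines it;
- either a 16%-33% probability above 50% at that dose, or at least 18 patients in the trial.

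Replace the sufficiently-large phrase in 5.1 with that reference. In the posterior table, mark doses with no patients as model predictions only. Separately, reconcile the printed reference dose in protocol 7.1 with Tables 7.1:2 and 10.6:1, and state in the SAP which value the analysis uses.

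The cost is SAP wording and a table footnote, plus a clarification of d*. No new data or design change is needed.
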